#### **Analysis of the Secondary/Exploratory Endpoints**

Linear mixed-effects regression models with random-intercept at the patient level will be used to examine the association of each outcome measure (OEF, CBF, and CMRO2) with demographical (sex and age) and laboratory data (Hb, reticulocyte count, bilirubin, LDH, Hb occupancy, oxygen dissociation curves, RBC deformability and

mitochondrial content). These models will be two-level and will account for repeated measures (0, 4, and 12 week measurements) nested within the same patient.

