## 1. Study Summary

Study Title	ESR-C007: The Effect of Voxelotor on Cerebral Hemodynamic Response in Children with Sickle Cell Anemia
Phase	Single-center, open label pilot study.
Study Design	This study is a pilot, open-label, single-arm study to evaluate the effect of voxelotor on cerebral hemodynamics, as measured by diffuse correlation spectroscopy and frequency domain near-infrared spectroscopy (DCS/FDNIIRS) in patients 4 -30 years of age with sickle cell anemia (SCA). We hypothesize that as hemoglobin increases due to voxelotor, cerebral blood flow (CBF) and oxygen extraction fraction (OEF) will decrease. To test this hypothesis, CBF, OEF, and oxygen metabolism (CMRO 2 ) will be assessed by DCS/NIRS in participants prior to, periodically throughout, and after 12 weeks of treatment with voxelotor. The results of this study will be used to inform a larger study.
Primary Objective	The primary objective of this research is to evaluate the effect of voxelotor on CBF, OEF and CMRO 2 in children with SCA as assessed by change from baseline in DCS/NIRS at 4 and 12 weeks.
Secondary Objective	The secondary objective of this research is to evaluate the correlation between changes in CBF, OEF and CMRO 2 and change in markers of anemia, hemolysis and RBC health at 4 and 12 weeks.
Research Intervention(s)/Interactions	
The study intervention is voxelotor, administered orally. It will be used for the approved indication of sickle cell disease. This is a single-arm study. There is no control intervention.
 
Drug Intervention: Voxelotor
 

• Voxelotor tablets: 300 or 500 mg, administered orally

• Voxelotor dispersible tablets: 100 and/or 300 mg, administered orally

 
All participants will receive voxelotor. Participants 12 years or older will take 1500 mg/day. Participants younger than 12 years of age will receive a dose based on their body weight to provide exposure corresponding to the adult dose of 1500 mg/day.

Study Population	We plan to recruit male and female children ages 4-30 years with sickle cell anemia (HbSS, HbS/β  thal) who are followed in the Pediatric Sickle Cell Program at Children's Healthcare of Atlanta

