### 3. Background

Sickle cell disease (SCD) is a genetic blood disorder that has profound effects on the brain. In the presence of chronic anemia, the brain microvasculature dilates in order to maintain adequate oxygen delivery to the tissue. As cerebral blood flow increases and the vasculature becomes maximally dilated, oxygen extraction fraction (OEF, defined as the difference between arterial and venous oxygen content) increases to keep up with metabolic demand. Unfortunately, this state of maximized response leaves the brain vulnerable and ill-equipped to adapt to increased metabolic demand; consequently, the tissue is susceptible to infarction when blood flow/volume are insufficient to maintain sufficient oxygen metabolism^11 (see **Figure 1**).

Chronic transfusion is used in patients with sickle cell disease to increase arterial hemoglobin concentration, which improves oxygen carrying capacity to the tissue. Recent work with MRI has confirmed that improved oxygen carrying capacity in turn reduces elevated cerebral blood flow (CBF) and oxygen extraction. Although cerebral oxygen metabolism appears to remain unchanged after transfusion, the return of oxygen extraction and blood flow to “normal” levels is thought to alleviate metabolic stress and improve the brain’s ability to respond to increased metabolic demand. Indeed, chronic transfusion therapy has been proven to reduce the incidence of both silent and overt infarcts in pediatric SCD patients. Despite the beneficial effects of transfusion, the therapy is not without significant risks, i.e., infection, iron overload, alloimmunization, and comes with a substantial burden to patients and their families. Moreover, the Silent Cerebral Infarct Multi-Center Clinical Trial (SIT) revealed that new silent infarct is prevented in only 1 out of every 13 children treated with transfusion therapy. Thus, *alternative therapeutic strategies that improve oxygen delivery to the brain without the risks associated with transfusion are needed to alleviate metabolic stress and reduce the risk of stroke.*

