Voxelotor (Oxbryta) is a new drug for patients with sickle cell disease that improves hemoglobin levels and reduces the incidence of worsening anemia. However, it is unclear whether this increase in hemoglobin is associated with a reduction in cerebral metabolic stress. ***In this work, we will determine the effects of voxelotor on cerebral hemodynamics.*** We hypothesize that as hemoglobin increases due to voxelotor, cerebral blood flow and oxygen extraction fraction will decrease, similar to the effects of blood transfusion. To test this hypothesis, measurements of brain blood flow, oxygen extraction, and oxygen metabolism will be made using the [name] Lab’s customized diffuse correlation spectroscopy and frequency domain near-infrared spectroscopy system (DCS/FDNIRS). These well-validated, non-invasive optical techniques utilize near-infrared

**Figure 1, Hypothesized mechanism of ischemic injury in pediatric sickle cell disease** (Adapted from Juttukonda et al., JMRI 2019). As anemia worsens, arterial oxygen delivery is reduced. To compensate for this reduction, the cerebrovascular dilates to increase cerebral blood flow (red). As vascular reserve is exhausted and CBF plateaus, oxygen extraction fraction (blue) increases to preserve oxygen metabolism (green). Eventually there is a mismatch between tissue metabolic demand (dotted black) and oxygen metabolism, and infarction ensues. Transfusion acts to increase oxygen delivery and is thought to relieve metabolic stress by reducing oxygen extraction and cerebral blood flow and improving vascular reserve. We hypothesize that the increase in hemoglobin caused by voxelotor will act in a similar fashion to reduce oxygen extraction fraction and blood flow.

light to penetrate deep into tissue (~1-2 cm) in order to estimate an average oxygen saturation of the microvasculature, i.e., capillaries, arterioles, and venules. Our preliminary results with DCS/FDNIRS applied to children with sickle cell disease suggest that the techniques are sensitive to alterations in blood flow and oxygen extraction in these patients associated with changes in hemoglobin.

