In a recently ancillary analysis of data from a Phase 2 Open Label Multicenter Trial (HOPE-KIDS 1; NCT02850406) voxelotor therapy in children with SCD was associated with improvements in RBC health as early as 12 weeks of treatment. Compared with pretreatment measures, RBC deformability performed at fixed shear stress and at varying osmolality showed sustained improvement. Upon gradual deoxygenation, RBC deformability under shear stress continued to improve with voxelotor. Furthermore, RBC sickling began at a much lower partial pressure of oxygen (pO2) compared with pretreatment values, which confirmed that voxelotor prevents ex vivo sickling in humans. In addition, the leftward shifts in oxygen dissociation curves (partial pressure p20 and p50) confirmed increased Hb-oxygen affinity with voxelotor treatment. ***In this work, we will explore how measurements of RBC health are associated with cerebral hemodynamics.*** We hypothesize that voxelotor modification of hemoglobin and improvements of RBC health will correlate with change in cerebral blood flow and oxygen extraction fraction. To test this hypothesis, measurements of RBC morphology, hemolysis, Hb modification, RBC deformability and adhesion will be made prior and during treatment period.

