## **17. Statistical Considerations, Data Management and Confidentiality**

### **17.1 Statistical Considerations**

#### **Statistical Hypothesis**

- Primary Endpoint: CBF and OEF are significantly lower at 4 and 12 weeks of treatment with voxelotor compared to pre-treatment levels. Paired t-test or Wilcoxon signed-rank test will be used to evaluate results, as patients are their own controls.
- Secondary Endpoints: The change in OEF and CBF from pre-treatment levels are significantly correlated with the change in hemoglobin. The change in OEF and CBF from pre-treatment levels are correlated with markers of hemolysis.

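### The random-intercept model for the secondary analysis, as listed, does not isolate the change-versus-change hemoglobin association that the secondary objective and hypothesis ask about

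*Combined protocol and SAP*

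**What the plan says.** Section 1 (Study Summary) states the aim in terms of change on both sides: "The secondary objective of this research is to evaluate the correlation between changes in CBF, OEF and CMRO" (the last term is CMRO₂) and change in markers of anemia, hemolysis and RBC health, at 4 and 12 weeks. Section 17.1 makes this a hypothesis for Hb: "The change in OEF and CBF from pre-treatment levels are significantly correlated with the change in hemoglobin". It adds one for hemolysis, where the marker is not itself called a change: "The change in OEF and CBF from pre-treatment levels are correlated with markers of hemolysis".

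The analysis is in Section 17.2, in the part that deals with secondary and exploratory outcomes. It reads: "Linear mixed-effects regression models with random-intercept at the patient level will be used to examine the association of each outcome measure", with sex, age and a list of laboratory measures as covariates. The visits enter only through the nesting: "These models will be two-level and will account for repeated measures (0, 4, and 12 week measurements) nested within the same patient". No equation is written. No visit effect, baseline term, change score or within/between split is named, and no sentence says which coefficient answers the Section 17.1 hypothesis.

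The primary analysis in Section 17.2 scales the relative change in OEF per g/dL of Hb change. That is an adjustment of the primary measure. It does not test whether the two changes are associated.

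**The concern.** A random intercept allows for correlation among a patient's measurements. It does not restrict the Hb coefficient to within-patient information. Three associations can feed that coefficient:

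- **Between patients.** Section 3 supplies the reason: "In the presence of chronic anemia, the brain microvasculature dilates in order to maintain adequate oxygen delivery to the tissue". More anemic patients would then have higher CBF at every visit, whatever happens to their Hb on treatment.
- **Shared on-treatment shift.** If Hb rises and the outcome falls in the whole cohort, a model without visit credits the fall to Hb, whether or not patients with larger rises had larger falls.
- **Within patients.** This is the association of a patient's change in outcome with that patient's change in Hb, which Section 17.1 asks about.

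The documents make the same direction plausible between and within patients, but not the same size. They also name a treatment effect other than the amount of Hb: earlier pediatric data "confirmed increased Hb-oxygen affinity with voxelotor treatment".

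At stake is the reading of a sizeable Hb coefficient. It could be reported as showing that patients whose Hb rose more had larger falls in CBF or OEF, although it can arise when individual changes are unrelated. The results are meant to inform a larger study.

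**Working it through.** **1. The plan's own figure.** Section 13.2 gives 40 evaluable patients and about 20% dropout: 40/(1 − 0.20) = 50, which reproduces the target. For the secondary analysis the documents give no alpha, power, effect size, SD or correlation.

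**2. What the listed coefficient estimates.** Read literally, the model is outcome = a + b·Hb + age + sex + patient effect + residual, at weeks 0, 4 and 12. With three balanced visits,

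b = (W·β_W + λ·B·β_B)/(W + λ·B), with λ = (1 − ICC)/((1 − ICC) + 3·ICC), W = 2·s_W², B = 3·(s_B² + s_W²/3).

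Here β_B is the between-patient slope and β_W the pooled within-patient slope. Without a visit term, β_W itself absorbs any shared shift. s_B and s_W are the between- and within-patient SDs of Hb, and ICC is that of the outcome.

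Example (assumed s_B = 0.8, s_W = 0.7, ICC = 0.5):
- λ = 0.5/(0.5 + 1.5) = 0.25
- W = 2 × 0.49 = 0.98
- B = 3 × 0.64 + 0.49 = 2.41
- between-patient share = 0.25 × 2.41/(0.98 + 0.25 × 2.41) = 0.60/1.58 = 38%

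Over s_B 0.8–1.2, s_W 0.4–1.0 and ICC 0.3–0.9 (all assumed), the share runs from 5% to 86%.

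**3. Simulation.** Outcome = β_B × baseline Hb + β_W × (visit Hb − baseline Hb) + shift × on-treatment + patient effect + residual. Only n = 40 comes from the documents. Assumed: baseline Hb SD 1 g/dL, Hb rise 1.0 (SD 0.8), Hb visit noise SD 0.3, patient SD of the outcome 0.8. There were 2000 trials per scenario, REML fits and two-sided 5% Wald tests. Triplets are for residual SD 0.3/0.6/0.9.

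True β_W = 0:

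| Scenario | Listed model, % significant | Mean coefficient |
|---|---|---|
| Neither mechanism | 5/5/5 | 0.00 |
| β_B = −0.5 | 15/34/42 | −0.04/−0.11/−0.16 |
| Shift = −0.3 | 91/32/15 | −0.14/−0.10/−0.08 |
| Both | 99/85/76 | −0.19/−0.22/−0.26 |

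Patient-mean and deviation terms plus visit give 4–7% in all four, with a mean within 0.01 of zero.

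True β_W = −0.3, mean estimate from the listed model:
- equal slopes, no shift: −0.30 (unbiased)
- β_B = 0: −0.28/−0.23/−0.20
- equal slopes plus shift −0.3: −0.44/−0.41/−0.39

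**4. Each added term does a different job.** Under a second set of assumptions (patient SD 4, residual SD 3, shift −2, β_W = 0), the deviation coefficient without visit still averages about −1.2 and is significant in 69–71% of trials. With visit it is significant in 5.0–5.5%. The split removes the between-patient part; visit removes the shared shift.

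**5. Sensitivity.** With baseline Hb SD 0.6 instead of 1.0, the β_B = −0.5 row drops from 15/34/42% to 7/12/13%. With an Hb-rise SD of 0.4 it rises to 17/39/54%. If the 0.3 visit noise is measurement or timing error and all slopes are −0.3, the deviation coefficient with visit averages about −0.21, against about −0.27 for the listed model.

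**The case against.** **The list may not be the model.** Section 17.2 writes no equation, and its covariate list is loose: it omits dense cells and adhesion, which the Section 2 table names, and includes RBC deformability, which that table does not. A reader might infer that visit is excluded. The text does not say so, which is why the point is confined to the model as listed.

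**The shared shift is part of the hypothesis.** Section 3 proposes that "as hemoglobin increases due to voxelotor, cerebral blood flow and oxygen extraction fraction will decrease". Adjusting for visit removes a fall that Hb itself carries, so visit adjustment is a choice of estimand. This stands. The high percentages in the shift rows are errors only if the coefficient is read as saying who responded more.

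**The coefficient need not be biased.** A reader might infer that the planned analysis is wrong. With equal slopes and no separate shift it is unbiased and clearly more powerful. The documents assert neither condition, but they do not contradict either.

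**Results are descriptive.** Section 17.2 says so, no alpha is set, and individual data will be listed by measure and time point. This lowers the severity and makes rejection rates a poor measure of harm. It does not remove the point: a descriptive estimate should still describe the quantity asked about, and Section 17.1 speaks of significant correlation.

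**Conclusion.** The point holds as a gap between question and model. The secondary objective and the Hb hypothesis concern within-patient change, and the listed model's Hb coefficient is a mixture that matches that target only under two conditions the plan does not state. The per-g/dL scaling in the primary analysis does not fill the gap.

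The size cannot be set from the documents. Every simulated figure except n = 40 rests on assumed inputs, depends strongly on the Hb spread, and is illustrative. Nor would the split model be unbiased in every circumstance: it attenuates when Hb is mismeasured or mistimed. Severity is modest for a descriptive pilot. Bilirubin sourcing, pairing of baseline measurements and alignment of endpoint wording are separate clarifications and are not part of this point.

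**What to change.** Write out the model equation in Section 17.2, then:

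1. Keep the planned model and label its Hb coefficient as the overall association.
2. Beside it, for Hb and the other CBC markers (scheduled with FDNIRS/DCS at D1, 4w and 12w in Section 5.2), report a model with the patient mean and the within-patient deviation as separate terms, once without and once with visit as a factor. State that the deviation coefficient without visit includes the shared on-treatment shift, and that with visit it answers whether patients whose Hb rose more had larger falls.
3. For markers with no week-4 sample, such as LDH and the RBC health measures, regress the baseline-to-week-12 change in outcome on the change in marker, with an intercept.
4. Report coefficients with confidence intervals, and do not read non-significance as no association.

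No new visits or samples are needed. The costs should be stated in the plan:
- **Power.** At equal slopes of −0.3 under the assumed inputs, power for the deviation term with visit is about 99/66/36%, against 100/99/90% for the planned model. The average 95% interval half-width is 0.12/0.24/0.37 per g/dL, against 0.08/0.14/0.18. Two-time-point change regression has about 96/49/25%.
- **Attenuation.** The deviation coefficient is pulled toward zero by error or mistiming in Hb.

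These costs are the reason to keep the planned model alongside.

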#### **Safety Analysis**

AEs will be coded by MedDRA terminology. Each AE will be counted once for a given participant. Severity, relationship to study drug, expectedness, dates, outcome, and duration of AEs will be reported.

#### **Baseline Descriptive Statistics**

Due to the anticipated small number of participants descriptive statistics will be used primarily to present the chart-extracted data. Summary of patient characteristics such as age, prior sickle cell complications, disease-modifying therapy, laboratory and radiology findings and outcomes will be presented. Descriptive analyses will involve calculation of proportions (frequencies) for categorical data. For continuous variables, mean and standard deviation (normally distributed data) or median and interquartile ranges (not normally distributed data) will be presented. Chi Square (or Fisher's Exact test as applicable) will be used to compare categorical variables presented as proportions of total. Student's t-test or one-way ANOVA will be used to compare continuous parametric variables and non-parametric variables, respectively. Aid in statistical analysis, if indicated, will be sought via the Emory Biostatistics Core.

#### **Tabulation of Individual Participant Data**

Individual participant data will be listed by measure and time point.

### **17.3 Data Management, Quality Assurance and Quality Control**

#### **Data Collection and Management Responsibilities**

Data collection is the responsibility of the study team under the supervision of the principal investigator. The investigator is responsible for ensuring the accuracy, completeness, legibility, and timeliness of the data reported.

All source documents will be completed in a neat, legible manner to ensure accurate interpretation of data.

Hardcopies of the study visit worksheets will be provided for use as source document worksheets for recording data for each participant enrolled in the study. Data recorded in the electronic case report form (eCRF) derived from source documents should be consistent with the data recorded on the source documents. Data will be recorded in password-protected database accessible only by PI and the study personnel. Any paper source documents will be stored in a locked cabinet in the Investigator's office.

### **Quality Assurance and Quality Control**

Study staff are trained extensively on the operation of the DCS/FDNIRS device prior to performing measurements. Documentation regarding device settings, sensor settings, and sensor positioning is completed at each measurement session. Periodic performance testing of the DCS/FDNIRS device is completed routinely with calibration standards.

The clinical site will perform internal quality management of study conduct, data collection, documentation and completion. The PI will check the quality and accuracy of data entry. The research lab conducts quality control on all its instrumentation and lab protocols.

Summarized data will be provided to GBT in study progress reports.

#### **17.4 Study Record Retention**

There is no set time for destroying information collected for this study. As this is an investigational, pilot study, we may use the data for future studies, and we also may need to access additional clinical information of the patient in the future as we delve deeper into the data and discover new aspects of the relationship between cerebral hemodynamics and clinical condition to explore.

#### **17.5 Protocol Deviations**

It is the responsibility of the Principal Investigator to use continuous vigilance to identify and report deviations to Emory IRB within 10 working days of identification of the protocol deviation, or within 10 working days of the scheduled protocol-required activity. All deviations must be addressed in study source documents, reported to the Emory University IRB and included in the study progress reports submitted to GBT. Protocol deviations must be sent to the reviewing Institutional Review Board (IRB) per their policies. The site investigator is responsible for knowing and adhering to the reviewing IRB requirements.

### **18. Provisions to Monitor the Data to Ensure the Safety of Participants**

Internal monitoring of the trial for protocol compliance and data accuracy will be the responsibility of the Research Administration QA/QI Analyst. The trial will be monitored for completion of the informed consent forms, clinical data capture forms, IP dispense logs and treatment-related adverse events not related to SCD. In addition, the credentials, delegation of authority and training logs will be monitored for study member. The monitoring will occur according to the following schedule:

- At least every six months while participants are receiving intervention and
- Annually while participants are in follow-up
- Close-Out Study Visit

Additional monitoring may be performed in the event of Serious Adverse Events if deemed necessary by the monitoring committee or if requested by the Principal Investigator.

This study will be conducted in compliance with the Aflac Cancer & Blood Disorders Center Data Safety Monitoring Board (DSMB) for Phase 1 and 2 pediatric studies. In brief, the role of the Data Safety Monitoring Board (DSMB) is to protect the interests of subjects and the scientific integrity for all Phase 1 and 2 studies. The DSMB consists of 7 members including a chair, a statistician, a pharmacist, and at least one external member.

The DSMB meets on a quarterly basis to review current study results, as well as data available to the DSMB from other related studies. The DSMB will provide recommendations for each study reviewed to change the study or to continue the study unchanged and will determine the frequency of future meetings.

Data and Safety Board reports for Institutional Review Boards will be prepared. The Principal Investigator assumes responsibility for assuring that the study is carried out in accordance with the DSMP.

DSMP Requirement	How this Requirement is Met	Frequency	Responsible Party(ies)
Site Monitoring at pre-determined intervals: The Principal Investigator has a responsibility to ensure that the study is following all aspects of the protocol.	
There should be a standard operating procedure to review data (whether a sample or 100%) at pre-determined intervals to ensure that there is adequate documentation of critical elements such as eligibility criteria. Monitoring is required at the following timepoints (but may be done more frequently):
 

study initiation

at least every six months while participants are receiving intervention and

annually while participants are in follow-up

	
At a minimum, a review is required annually when no one has been enrolled or the study is in long term follow up. Additional interim monitoring at least once every 12-24 weeks based on the site activity, and more as needed, to include the possibility of remote monitoring.
	
Delegate a responsible party for each requirement below*. Self-assessment is NOT acceptable. An experienced, knowledgeable person who is independent of the study team should serve as monitor. A Contract Research Organization (CRO) may be used. Consult the IRB Office regarding acceptable qualifications for the independent monitor, if not using an outside expert such as a CRO.

Real-time review of participant data during initial data collection.	Inclusion/Exclusion Checklist is completed by the CRC and reviewed by the PI for approval and signoff. The CRC will also signoff	This is completed when study subjects enroll	Study team and PI
100% review of regulatory files	Regulatory binder will be created to house all Regulatory documents for review. Regulatory files will be reviewed by monitor at monitoring visits.	Start of study, close out and as necessary in between	Team coordinators, QA/QI Analyst

100% review of consent forms	Per Aflac policy, all consents are reviewed in real time by 2 separate coordinators. The first review is within 5 days of the consent. The next review is within 5 days of the first review but within 10 days of the consent date. Consents will be reviewed by monitor at monitoring visits.	As consents are signed	Team coordinators QA/QI Analyst
Review of credentials, training records, the delegation of responsibility logs (if applicable)	Study training logs are kept in the Regulatory Binder for review with the upkeep of the coordinators. This information will be reviewed by monitor at monitoring visits.	Reviewed every time there are study team changes as well as study amendments	Team coordinators QA/QI Analyst
Comparison of case report forms (CRF) to source documentation for accuracy and completion	Data will be stored on [name]'s lab's server. The assigned monitor will compare data in the study database to the source data on the CRFs. Discrepant data and queries will be sent to the study team who will be required to respond to each item. CRF documentation will be reviewed by monitor at monitoring visits.	Yearly Review	[name] Lab, CHOA QA/QI Analyst
Review of documentation of all adverse events	The PI will have oversight on the documentation of AE's which will be logged and tracked by the study Coordinator and kept in the subject's study chart. AE documentation will be reviewed by monitor at monitoring visits.	Every time an AE occurs the Study Coordinator will log it. Monitor will review at specified monitoring intervals.	PI, Team Coordinators, QA/QI Analyst
Monitoring of critical data points (eligibility, study endpoints, etc.)	Data Collection of critical data points is the responsibility of the study coordinators under the supervision of the principal investigator. The coordinators are responsible for ensuring accuracy, completeness, legibility, and timeliness of the data reported. The monitor will	Eligibility will be confirmed at time of patient enrollment. Study endpoints will be reviewed at end of each treatment period.	Principal Investigator, Team Coordinators, and QA/QI Analyst

	review critical data points at monitoring visits. The PI will have oversight over all data collected for the study and will review all monitoring reports upon the completion of a monitoring visit.		
Laboratory review of processing and storage of specimens	Coordinators will process labs. Labs are typically shipped same day of collection but can be stored on site as well.	If samples are stored, they are reviewed at the visits and close-out visit	[name] Lab, Team Coordinators, QA/QI Analyst
Assessment of laboratory specimens stored locally	The specimens will be stored in [name] lab (HSRB E169)	Yearly	[name] Lab
Test article accountability review	[name] lab is responsible for device maintenance and calibration. Calibration records will be reviewed by monitor at monitoring visits.	Calibration will be done prior to each measurement	[name] Lab, QA/QI Analyst
Accountability logs, dispensing records, and other participant records	All IP and IP logs are monitored and housed with the Research Pharmacist within NCoup. IP logs will be reviewed by monitor at monitoring visits.	Will be monitored at least once monthly, more frequently if an active patient is on the study	Research Pharmacist, QA/QI Analyst
For FDA regulated studies, the following requirements apply:	How this Requirement is Met	Timing, frequency, and intensity of monitoring	Responsible Party(ies)
Monitoring methods (may include centralized, on-site, and self-monitoring)	Previously, CTAC did a review after the first 10 subjects and the results of that were provided in the comments of the CR already. The QA/QI Analyst will be monitoring this study going forward.	As per protocol	QA/QI Analyst

\*For international studies, you are required to engage a CRO that is working in the site country and/or to consult with Emory's legal counsel regarding compliance with the country's clinical research regulations.

